6.2.1 Adverse events (AEs).....	21
6.2.2 Serious adverse events (SAEs).....	21
6.3 Follow-up of adverse events.....	22
7. STATISTICAL ANALYSIS	23
7.1 Primary study parameters	23
7.2 Secondary study parameter	23
7.3 Other study parameters.....	23
8. ETHICAL CONSIDERATIONS	24
8.1 Regulation statement	24
8.2 Recruitment and consent.....	24
8.3 Benefits and risks assessment, group relatedness	24
8.4 Compensation for injury	25
8.5 Incentives.....	25
9. ADMINISTRATIVE ASPECTS, MONITORING AND PUBLICATION	26
9.1 Handling and storage of data and documents	26
9.2 Amendments.....	26
9.3 Annual progress report.....	26
9.4 Temporary halt and (prematurely) end of study report.....	27
9.5 Public disclosure and publication policy.....	27
10. REFERENCES	28

LIST OF ABBREVIATIONS AND RELEVANT DEFINITIONS

3D	Three Dimensional
AE	Adverse Event
AF	Atrial Fibrillation
AR	Adverse Reaction
CMR(l)	Cardiovascular Magnetic Resonance Imaging
CV	Curriculum Vitae
ECV	Extra Cellular Volume
HF	Heart Failure
IC	Informed Consent
LA	Left Atrial
LGE	Late Gadolinium Enhancement
LV	Left Ventricular
LVEF	Left Ventricular Ejection Fraction
METC	Medical research ethics committee (MREC); in Dutch: medisch-ethische toetsingscommissie (METC)
MVI	Mitral Valve Insufficiency
PC-	Phase Contrast Magnetic Resonance Angiography
MRA	
PH	Pulmonary Hypertension
(S)AE	(Serious) Adverse Event
WMO	Medical Research Involving Human Subjects Act; in Dutch: Wet Medisch-wetenschappelijk Onderzoek met Mensen

SUMMARY

Rationale: Patients with mitral valve insufficiency (MVI) suffer from left atrial (LA) remodeling. Atrial fibrosis is part of this remodeling process. The presence of atrial fibrosis is associated with an increased risk of atrial fibrillation (AF), heart failure (HF), pulmonary hypertension (PH), a reduced quality of life and eventually a shorter life expectancy.

Currently, mitral valve repair surgery is the ultimate treatment for severe primary MVI. The main indications and timing for surgery are severe MVI with symptoms or left ventricular dysfunction. However, the role of atrial fibrosis in this process remains undetermined despite its well-recognized clinical implications.

Characterization of atrial fibrosis patterns in MVI patients might be potentially valuable for the indication and timing of mitral valve repair surgery in order to improve clinical outcomes.

With the introduction of cardiac MRI for the assessment of atrial fibrosis in AF patients suffering from extensive LA remodeling without MVI, the identification of appropriate patients and therapy stratification for cardiac ablation and the associated clinical outcome was significantly improved.

To date, however, MVI patients suffering from LA remodeling have hardly been studied using these new imaging techniques. Therefore, we intend to combine advanced cardiac MRI and post-processing techniques prior to and after mitral valve repair surgery to gain more insight in the clinical implications of atrial fibrosis in this patient population.

It is hypothesized that the atrial fibrosis surface area paradoxically will increase after mitral valve surgery because of global shrinkage of the LA caused by the reversed remodeling process.[1] As a consequence, more frequently atrial fibrosis related events including (paroxysmal) AF, may be observed in these patients.

Objective: To assess the effects of (reduced) volume overload on the left atrial wall texture (presence, amount and location of atrial fibrosis) and associated geometry and function in patients with MVI, prior to and after mitral valve repair surgery.

Study design: Single center pilot study.

Study population: The research population consists of MVI patients scheduled for elective surgical mitral valve repair (N=20) according to the current European guideline criteria.

Image data from non-MVI/AF age-sex matched controls (N=10), retrieved from an existing database will be used for reference purposes. These controls have undergone the same MRI scan protocol for another indication.

Main study parameters/endpoints:

The main study parameters are:

1. Severity of MVI prior to and after surgery (defined as regurgitation volume in ml)
2. Left atrial remodelling prior to and after surgery
 - Left atrial volume
 - Calculated left atrial sphericity
 - Estimated wall tension (wall thickness, radius, pulmonary wedge pressure)
 - Mitral regurgitation flow measurement (quantitative)
3. Presence and distribution patterns of LA fibrosis
 - Quantification of fibrosis surface (severity)
 - Geometric distribution of fibrosis (localization)
4. Blood flow patterns in the left atrium (4D flow)
 - Flow velocity (mean and peak)
 - Static fraction
 - Kinetic energy

Nature and extent of the burden and risks associated with participation, benefit and group relatedness:

This is a cardiac MRI study with the use of contrast media (Gadolinium). There is no associated additional risk expected for participating patients. There are no direct benefits for individuals participating to our study.

1. INTRODUCTION AND RATIONALE

Patients with mitral valve insufficiency (MVI) frequently suffer from left atrial (LA) remodeling, caused by volume overload and subsequent atrial dilatation.[1]

The associated myocardial stretch and increased wall tension, trigger a cascade of pathways leading to the occurrence of atrial fibrosis as part of the remodeling process (*Figure 1*).[2] The clinical relevance of this atrial fibrosis, is that its presence is associated with an increased risk of atrial fibrillation (AF), heart failure (HF), pulmonary hypertension (PH), a reduced quality of life and eventually a shorter life expectancy.[3, 4] In addition, in patients suffering from atrial fibrillation (AF), the presence and amount of LA fibrosis was found to be a strong predictor for ablation efficacy and long-term outcome.[5, 6]

In daily clinical practice, MVI is managed either by medical or surgical therapy.[7] However, since medical therapy is often not sufficient for patients with severe primary MVI, surgical intervention remains the ultimate treatment option for these patients. In general, valve repair is the preferred type of surgery, since it has better clinical results compared to valve replacement.[8]

Currently, the indication and timing for valve surgery is mainly based on the severity of MVI and the presence of symptoms and/or severity of left ventricular dysfunction.[9]

For clinical decision making and patient stratification for mitral valve surgery, the presence of atrial fibrosis is currently not taken in account, despite its well-recognized clinical implications.

Detection of atrial fibrosis patterns in patients with severe MVI, however, may be potentially valuable for the indication and timing of mitral valve repair surgery to improve clinical outcomes. Improved insight into atrial fibrosis patterns and changes after mitral valve repair due to reverse remodeling, may help clinicians in their clinical decision making and timing for surgery.

Today, quantification of atrial fibrosis can be routinely performed using cardiac magnetic resonance imaging (CMR) techniques and advanced post-processing tools, offering non-invasive tissue characterization in thin-walled structures.[6]

To date, MVI patients suffering from LA remodeling have hardly been studied using these new imaging techniques. Therefore, in this study, we want to combine advanced cardiac MRI and

post-processing techniques prior to and after mitral valve repair surgery to gain insight on the clinical role and predictive value of atrial fibrosis in this patient population.

In addition, we aim to assess the effects of (reduced) volume overload on atrial wall texture, geometry and function.

It is hypothesized that the atrial fibrosis surface area paradoxically will increase after mitral valve surgery because of global shrinkage of the LA caused by the reversed remodeling process.[1] As a consequence, more frequently atrial fibrosis related events including (paroxysmal) AF, may be observed in these patients.

With this insight, CMR can become clinical valuable for the indication and timing of surgical intervention in these patients. Surgical therapy might be renounced for example when a substantial increase of fibrosis surface is expected post-surgically causing a higher risk for AF, HF, PH and a reduced quality of life. On the contrary, surgical therapy might be considered in an earlier stage of disease when the amount of fibrosis is still limited regarding its expected post-surgical development.

[figure not shown]

Figure 1. Pathway to structural LA remodeling caused by a pathological trigger.

2. OBJECTIVES

Primary Objective:

To assess

- the effects of (reduced) volume overload on the left atrial wall texture (presence, amount and location of atrial fibrosis) and associated geometry and function in patients with MVI, prior to and after elective mitral valve repair surgery.

Secondary Objectives:

To assess;

- the value of LA fibrosis in stratification and timing of mitral valve repair surgery.
- the impact of atrial fibrosis on myocyte contractile function (atrial strain, quantified by CMR).
- whether left ventricular (LV) volume overload results in increased extra cellular volume (ECV) and whether this is reversible after mitral valve repair surgery.
- the impact of LA remodeling on right atrial (RA) function and tissue characteristics.
- the predictive value of LA fibrosis for outcomes of AF and atrial function during post-surgical follow up

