3. STUDY DESIGN

This study is designed as a single center pilot study. The aim of this study is to assess the role of left atrial fibrosis and its characteristics prior to and after mitral valve repair surgery in MVI patients.

Study subjects that will be included are MVI patients who meet the criteria for mitral valve repair surgery and are on the waiting list for elective surgery. Exclusion criteria are: AF, history of cardiac surgery, comorbidities, MRI contra-indications. The study subjects are recruited from the Amsterdam UMC surgical waiting list.

The study subjects will visit the AmsterdamUMC hospital (Location VUmc) two weeks prior to mitral valve repair surgery for a CMR scan. This visit will start with checking in- and exclusion criteria using questionnaires regarding medical history and MRI safety. The total duration of the visit, including the CMR scan, will be approximately two hours.

[figure not shown]
Two weeks later the subjects will undergo mitral valve repair surgery (Location AMC). During anesthesia, a Swan-Ganz catheter will be used for hemodynamic monitoring. This Swan-Ganz catheter is part of the standard care for mitral valve repair surgery.

At three months follow-up, subjects will visit the AmsterdamUMC hospital (Location VUmc) for a second CMR scan to assess reversed atrial remodeling and amount of fibrosis.

Image data from age and gender matched controls will be retrieved from an existing database. The patients in this database have undergone the same MRI scan protocol (for a different medical indication) as scheduled for our study population. Only data from patients without MVI and AF will be used from the database for reference. Absence of MVI and AF will be confirmed by checking ECGs and echocardiography of the control patients.

See *figure 2* for a schematic representation of the study design.

Figure 2. Schematic representation of the study design: Left atrial remodeling in MVI

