4. STUDY POPULATION

4.1 Population (base)

The research population consists of MVI patients scheduled for elective surgical mitral valve repair conform the current guideline criteria.

These patients will be recruited from the surgery-waiting list / database of the AUMC after they have been accepted for surgery by a multidisciplinary heart team.

Data from a control group of non-MVI/AF age-sex matched controls (N=10) will be retrieved from an existing database. These controls have undergone the same MRI scan protocol for a different medical indication.

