4.2 Inclusion criteria

The following patients will be targeted for inclusion.

- Patients that meet the criteria for elective mitral valve repair surgery according to the European clinical guidelines (class I recommendation);
 - Symptomatic, chronic severe mitral valve insufficiency due to degenerative valve disease with a left ventricular ejection fraction (LVEF) >30%.
 - Asymptomatic, chronic severe mitral valve insufficiency due to degenerative valve disease with a LVEF <60% and/or a left ventricular end-systolic diameter (LVESD) >45 mm.

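### The secondary objective on the value of LA fibrosis for stratification and timing of surgery cannot be answered: no MVI patient goes unoperated or deferred, and no timing comparison is planned

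*Combined protocol and SAP*

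**What the plan says.** Section 2 gives five secondary objectives. The first is to assess "the value of LA fibrosis in stratification and timing of mitral valve repair surgery", with no exploratory qualifier. The fifth concerns how well LA fibrosis predicts AF and atrial function during follow-up after surgery.

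Section 4.1 defines who is studied: "The research population consists of MVI patients scheduled for elective surgical mitral valve repair conform the current guideline criteria". They are recruited "after they have been accepted for surgery by a multidisciplinary heart team". Section 4.2 requires a class I guideline indication, which covers symptomatic patients with LVEF above 30% and asymptomatic patients with LVEF below 60% and/or LVESD above 45 mm. Section 4.4 sets the number at 20, all surgical.

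Under section 3 each patient attends "two weeks prior to mitral valve repair surgery for a CMR scan", is operated on, and returns at three months "for a second CMR scan to assess reversed atrial remodeling and amount of fibrosis". The only other participants are 10 database controls without MVI or AF, used for reference.

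Section 1 describes the decisions that such knowledge might inform: "Surgical therapy might be renounced for example when a substantial increase of fibrosis surface is expected post-surgically". It also raises the possibility of earlier surgery while fibrosis is still limited. Section 7.1 names correlation analyses and a Fisher exact test in general terms and ties neither to this objective.

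**The concern.** The value of a marker for a treatment decision lies in how outcomes under the alternatives differ across levels of the marker. For stratification the alternatives are operating and not operating (or deferring). For timing they are operating earlier and operating later in the disease. This study observes one course only: repair in patients who already qualify for it.

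What it can show is whether preoperative fibrosis goes along with the findings three months after repair. Suppose patients with more fibrosis do worse. That would fit equally well with three accounts: they should have been operated on earlier, they should not have been operated on, or surgery helped them but they started from a worse position. Reported under this objective, such an association could be taken as evidence on indication or timing. One of the implications raised in section 1 is forgoing an operation for which the patient has a class I indication, so the limit of inference should be in the plan.

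**Working it through.** The plan gives no figure for this objective: the 20 in section 4.4 is a pilot number without effect size, SD or power. The check is therefore one of identifiability, taken separately for the two halves.

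**Inputs.** 20 MVI patients (section 4.4); all accepted for surgery before recruitment (section 4.1); all with a class I indication (section 4.2); all operated on (section 3); controls without MVI (sections 3 and 4.1).

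**1. Whether to operate.** Let Y be a follow-up outcome, F preoperative fibrosis and S = 1 if operated on, 0 if not. The model needed is

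E(Y) = b0 + b1·F + b2·S + b3·F·S,

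where b3 expresses how the effect of surgery depends on fibrosis. In this study S = 1 for all 20, so the four columns of the design matrix are 1, F, 1 and F. The rank is 2 of 4, and the model reduces to

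E(Y) = (b0 + b2) + (b1 + b3)·F.

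Only the sum b1 + b3 can be estimated. Any observed slope is compatible with b3 positive, zero or negative. The rank does not depend on the number of patients, so enlarging the study changes nothing. The controls cannot supply S = 0, because they do not have the disease for which surgery is considered.

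**2. When to operate.** Two quantities must be kept apart.

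- *Scan-to-surgery interval.* Section 3 fixes it at two weeks for everyone. Put in place of S, this constant again gives rank 2 of 4. But this interval is not what the objective means by timing.
- *Stage of disease at surgery.* This is how section 1 uses the word: severity of MVI, symptoms, left ventricular dysfunction. Section 4.2 lets it vary, so the rank argument does not apply.

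The timing half fails on other grounds. First, no comparison by stage is planned: section 7 has none, and section 5.1 lists no outcome for judging a timing rule. Second, everyone already meets current criteria, so surgery before those criteria are met lies outside the data. Third, stage at surgery is defined by symptoms and ventricular function, the same features that drive the indication and bear on outcome, so a comparison across stages would be confounded by indication.

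**3. What remains.** The slope b1 + b3 can be estimated in operated patients. It is a prognostic association, and for AF and atrial function it is already the subject of the fifth secondary objective.

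**The case against.** The strongest reply is that the objective is being read too strictly. It states no treatment contrast and no decision rule, the study is called a pilot, and section 1 speaks of insight into the clinical role and predictive value of fibrosis. Describing how fibrosis relates to findings after repair is a fair first step. It is, and the proposed wording keeps it. But the objective as written speaks of stratification and timing, not prediction after repair. A pilot label excuses low precision, not a comparison that the design lacks.

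Three further points stand and limit the concern.

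- A reader might infer from section 3 that all patients are operated on at the same time, so that none of the 20 carries any information on timing. The documents do not support that. Only the interval between scan and surgery is fixed. Stage can differ under section 4.2, and section 5.7 allows that operations may be delayed by COVID-19 measures. Such variation is unplanned, and waiting time is not among the parameters listed in section 5.1, but it is not nil.
- A reader might infer that the protocol claims surgery will be withheld or advanced on the strength of this study. Section 1 is hedged throughout and reads as rationale for later use. Nothing says that the scan result affects whether or when a participant is operated on.
- The controls are offered only as an imaging reference. The protocol never presents them as an unoperated comparator.

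**Conclusion.** The objective is wrong as written. For deciding whether to operate, the value of LA fibrosis is not estimable at any sample size, because surgery does not vary among MVI patients. This rests only on the recruitment and treatment described in sections 3, 4.1, 4.2 and 4.4, and needs no assumption about effect size or variance.

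For timing the conclusion is weaker: stage may vary, but there is no planned comparison, nobody is operated on ahead of current criteria, and any contrast would be confounded. It would go too far to call timing strictly inestimable.

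How precisely 20 patients can estimate a prognostic association is a separate question and plays no part here. The consequence is confined to what the study may claim. The imaging, the visits and the other objectives are unaffected.

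**What to change.** 1. In section 2, delete this objective or merge it with the fifth. Suggested wording: to estimate, in operated patients only and as a hypothesis-generating analysis, the association between preoperative LA fibrosis and LA volume, LA function and AF at three months.

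2. In section 7, name the analysis. For LA volume and function, regress the 3-month value on preoperative fibrosis and on the baseline value of the same outcome. AF is excluded at entry (section 4.3), so it needs no baseline term. It is not listed in section 5.1, however, so how it is recorded at three months should be stated.

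3. Do not correlate baseline fibrosis with change in fibrosis. With F0 and F1 the values before and after surgery, Cov(F0, F1 − F0) = Cov(F0, F1) − Var(F0). With equal variances and a correlation below 1 this is negative even if surgery has no effect, because the baseline is part of the change score.

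4. Add to section 7 that no conclusion on the indication for, withholding of, or timing of surgery will be drawn from this study.

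5. Optionally, recast the section 1 sentences on forgoing or advancing surgery as questions for a later study that includes unoperated or differently timed MVI patients. They are already hedged, so this is minor.

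The change is to wording and analysis text. It needs no extra patients or visits. The downside is a less ambitious stated objective.

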4.4 Sample size calculation

This study is designed as a pilot study, since we are the first to assess the effect of LA fibrosis and its characteristics prior to and after mitral valve repair surgery.

Therefore we aim to include;

- 20 patients with MVI which are admitted to mitral valve repair surgery

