7. STATISTICAL ANALYSIS

7.1 Primary study parameters

CMR qualitative and quantitative analyses will be performed on a dedicated work-station with counseling of investigators experienced in the post-processing of CMR techniques.

The included data will be presented as mean \pm standard deviation. Ratios will be given for statistical assessment of non-continuous variables. Correlation analyses will be used to analyze differences between continuous parameters. Confidence intervals (95%) will be used and a $p < 0.05$ will be considered statistically significant. Fisher exact test will be performed to verify significance, risk ratio (RR) and 95% confidence intervals. SPSS 26.0 (SPSS Inc, Chicago, IL) for Windows is used to assess statistical analyses.

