7.2 Secondary study parameter

Analysis of the obtained bloodsamples for fibrosis associated biomarkers will be performed by the department of laboratory medicine and pathology of the AmsterdamUMC (location AMC).

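### Nothing in the analysis plan brings in pre-operative atrial function, so an unadjusted correlation could not show that LA fibrosis adds predictive information about atrial function after repair

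*Combined protocol and SAP*

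**What the plan says.** The secondary objectives in section 2 include "the predictive value of LA fibrosis for outcomes of AF and atrial function during post-surgical follow up" and, separately, "the impact of atrial fibrosis on myocyte contractile function (atrial strain, quantified by CMR"). This point concerns atrial function only. Patients with AF are excluded at entry, so the AF part raises a different question.

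Section 7.1, on the primary parameters, says: "Correlation analyses will be used to analyze differences between continuous parameters". For categorical data it says: "Fisher exact test will be performed to verify significance, risk ratio (RR) and 95% confidence intervals". A p-value below 0.05 "will be considered statistically significant"; whether the tests are two-sided is not stated.

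Section 7.2, on the secondary parameter, covers only where the laboratory work is done: "Analysis of the obtained bloodsamples for fibrosis associated biomarkers will be performed by the department of laboratory medicine and pathology". Section 7.3 is descriptive. No section mentions regression, partial correlation, a covariate, baseline adjustment or change from baseline.

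CMR is done before surgery and again at three months (sections 3 and 5.2), with cine imaging in the scan protocol. Section 4.4 sets the size at "20 patients with MVI which are admitted to mitral valve repair surgery", justified by pilot status alone. Section 5.1.1 lists no atrial function measure among the main or secondary parameters.

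**The concern.** A patient whose atrium works poorly before surgery may well have one that works poorly three months later. If fibrosis is also more extensive in such patients, pre-operative fibrosis and post-operative function will be correlated whether or not fibrosis says anything that pre-operative function does not already say. An unadjusted correlation cannot separate these two situations.

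This matters because sections 1 and 2 look to fibrosis to inform the indication for and timing of surgery. A marker used that way should add to what the same pre-operative scan already shows. A significant unadjusted correlation, with 0.05 as the stated threshold, could be read as evidence of that when it is not.

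**Working it through.** **The plan's own figure.** There is nothing to reproduce. The target of 20 patients comes with no power, effect size or standard deviation.

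**Inputs**
- n = 20 (section 4.4) and significance level 0.05 (section 7.1), taken as two-sided.
- r(F,P), fibrosis with pre-operative function: not in the documents; assumed -0.3 to -0.6.
- r(P,Y), pre-operative with three-month function: not in the documents; assumed 0.5 to 0.8.
- Fibrosis adds nothing once pre-operative function is known, so the partial correlation of F and Y given P is zero.

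**Induced correlation.** A zero partial correlation means r(F,Y) = r(F,P) × r(P,Y). In the middle case this is -0.5 × 0.7 = -0.35.

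**Critical values at n = 20**, from t / √(t² + df):
- simple correlation, df = 18, t = 2.101: 0.444
- partial correlation, df = 17, t = 2.110: 0.456

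**How often each test is significant.** Trivariate normal data were simulated, with at least 40,000 studies per case. The simple test uses t = r√(18/(1 − r²)). The adjusted test uses the partial correlation (r_FY − r_FP·r_PY) / √((1 − r_FP²)(1 − r_PY²)) on 17 df, which is the same test as that of fibrosis in a regression of Y on F and P.

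| r(F,P) | r(P,Y) | induced r | simple | adjusted |
|---|---|---|---|---|
| 0 | 0.7 | 0 | 5% | 5% |
| -0.3 | 0.5 | -0.15 | 10% | 5% |
| -0.3 | 0.8 | -0.24 | 18% | 5% |
| -0.5 | 0.7 | -0.35 | 34% | 5% |
| -0.6 | 0.8 | -0.48 | 60% | 5% |

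With weaker links (-0.2 and 0.4) the simple test is significant in 6%.

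**Fewer evaluable patients.** Data of withdrawn subjects are deleted (section 5.4) and poor images are excluded (section 5.2). With an assumed n = 16, the middle case gives 27% against 5%.

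**Change scores.** Correlating fibrosis with the raw change, assuming equal variances, still gives 13% in the middle case at n = 20. It is not a full remedy.

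**Measurement error in pre-operative function.** Hold the observed correlations at -0.5 and 0.7 and let the baseline measure have reliability ρ. The correlation of F and Y is then -0.35/ρ, and the partial correlation given observed P is (-0.35/ρ + 0.35) / √(0.75 × 0.51).

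| assumed ρ | r(F,Y) | partial r | adjusted test significant |
|---|---|---|---|
| 0.9 | -0.389 | -0.063 | 6% |
| 0.8 | -0.438 | -0.141 | 9% |
| 0.7 | -0.500 | -0.243 | 17% |

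The 5% in the first table therefore holds only if pre-operative function is measured without error.

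**Power of the adjusted test at n = 20**, for the -0.5 and 0.7 case without measurement error: about 24% for a true partial correlation of 0.3 in size, 62% for 0.5 and 81% for 0.6.

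**The case against.** **The plan does not assign simple correlation to this objective.** A reader might infer that the plan has chosen unadjusted correlation here. It has not: the sentence stands under the primary parameters, and the term does not exclude partial correlation. This stands. Correlation is the only named method that could serve a continuous outcome, but the link is an inference. If it is wrong, the objective has no analysis at all, and the same addition is needed.

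**34% is not a false-positive rate of the correlation test.** In the simulated case the marginal correlation really is -0.35, so the simple test is right to detect it. This stands too. The figure is an error rate only for a claim of value beyond pre-operative function, and section 2 does not use words such as independent or added.

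**Pre-operative function may lie on the causal path.** If fibrosis impairs contraction, adjustment removes part of its effect. The assumed correlations fit that account as well as confounding. This is a good reason to keep the unadjusted result in the report, not to rank it below the adjusted one. It does not let the unadjusted result support a claim of added value.

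**The premises are not established.** The documents give no direction or size for the link between fibrosis and function. They expect the atrium to shrink after repair (section 1), so carry-over of function is an open question. This is why the size is given as a range that includes no inflation.

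**Current surgical decisions rest on other factors.** Section 1 names MVI severity, symptoms and left ventricular dysfunction, not atrial function. The proposed model would therefore not show added value over those factors.

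**This is a 20-patient pilot.** Section 4.4 says "This study is designed as a pilot study, since we are the first to assess the effect of LA fibrosis" and makes no power claim. That limits the weight of the point, but section 7.1 still sets a significance threshold.

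**Conclusion.** The point holds in a limited form. Nothing in the plan uses pre-operative atrial function when fibrosis is judged as a predictor of atrial function after repair, and an unadjusted correlation alone could not show that fibrosis adds to it. If there is no added value, such a correlation would be significant in about 10% to 60% of 20-patient studies over the assumed ranges, and in 34% in the middle case. Those figures rest on two correlations that the documents do not give, and on both links being present. If fibrosis is unrelated to baseline function, the rate is 5%.

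Two stronger readings are not supported. The documents do not show that a correlation found in this study would be spurious, because it would be a valid description of marginal association. Nor do they show that pre-operative function strongly determines function at three months.

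**What to change.** Add to section 7, for this secondary objective:

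1. Name one atrial function measure as the outcome, for example the CMR atrial strain already mentioned in the objectives. Testing several measures would add multiplicity that 20 patients cannot support.
2. Regress its three-month value on pre-operative LA fibrosis and on the pre-operative value of the same measure.
3. Report the adjusted coefficient with its 95% CI alongside the unadjusted correlation.
4. Rest any claim of added predictive value on the adjusted result only, and label it exploratory.

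The cost is wording and one degree of freedom: the critical |r| rises from 0.444 to 0.456, and the |r| detectable with 80% power (Fisher z approximation) from 0.59 to 0.60. The baseline scan is already planned. Two limits remain and should be stated with the result. Measurement error in baseline function leaves some residual confounding. The adjusted estimate also leaves out any effect of fibrosis already expressed through pre-operative function, which is why both results are reported.
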